#### A. Opioids Analgesics and side effects

Although the concept of "multimodal analgesia" of using different drugs with different mode of action to interfere with the pain pathway, such as using non-opioid adjuvants (e.g. NSAIDS, steroids, regional anesthesia) have been developed to improve postoperative pain management, opioids remain the cornerstone of treatment of postoperative pain. Opioids produce analgesia and other effects by binding to specific opioid receptors in the peripheral and central nervous system. Three types of opioid receptors and their subtypes have been discovered: mu, delta, and kappa receptors. The most commonly used opioids bind to mu receptors. The mul receptor is responsible for the production of opioid-induced analgesia, whereas mu2 receptors provoke respiratory depression, cardiovascular effects, and inhibition of gastrointestinal motility commonly seen with opioids.[8-10] Sole reliance on opioids is often inadequate and leads to significant side effects.[11]

Adverse events associated with opioids include an increased risk of postoperative urinary retention (POUR). It has been shown in multiple studies that systemic opioids contribute to urinary retention. Opioids inhibit the release of acetylcholine and thereby decreases the parasympathetic output to the detrusor and thus bladder contractility. This effect is directly related to the dose of opioids given and the opioid sparing multi-modal analgesia has been shown to reduce urinary retention.[12, 13] The true incidence of POUR is unclear but is estimated to vary between 5-70%.[14]

The opiates or its analogues decrease the sensation of bladder fullness by partially inhibiting the parasympathetic nerves that innervate the bladder. In addition, opiates have been shown to increase the sphincter tone of the urinary bladder via sympathetic overstimulation, resulting in increased bladder outlet resistance. The combination of decreased sensation of fullness and increased outlet resistance increase the risk of urinary retention. Studies suggest that the halflife of the opioid used has an impact on urinary function and risk of retention.

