#### G. Data Analysis

Naloxegol group and placebo group will be compared for balance of baseline characteristics using standard descriptive statistics (i.e., mean  $\pm$  standard deviation, median [Q1, Q3], or N (%) as appropriate) and standardized difference. The standardized difference is the difference in means or proportions divided by the pooled standard deviation. Any covariable with a standardized difference greater than 0.2 in absolute value will be regarded as a potential confounder, and will be adjusted for when comparing Naloxegol and placebo groups on all the outcomes.

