#### Secondary and exploratory analysis.

We will test the following three secondary hypotheses: subjects who received Naloxegol 25 mg given once in the morning every day will have (1) fewer opioid-related side effects, (2) less need of indwelling catheterization determined by the residual volume to be above 400 ml, and (3) improved quality of recovery as compared to placebo.

The two groups will be compared on the incidence of any opioid-related side effects using a logistic regression. The frequency, severity, and bothersomeness for each of the 12 opioid-related side effects on POD 1 and 2 will be summarized. We will compare the two groups on incidence (any versus none) of need for indwelling urinary catheterization (defined as residual urine volume > 400 ml) using logistic regression. The two groups will also be compared on the Quality of Recovery scale measured on POD 2 (or day of discharge if it occurs earlier) using a linear mixed model with an autoregressive correlation structure. All the analyses will be adjusted for imbalanced baseline characteristics, if any. The hypothesis-wise 2-sided type I error for each of the secondary outcome will be controlled at 0.017 (i.e., 0.05/3, Bonferroni correction).

In addition, we will summarize the following exploratory outcomes, including satisfactory of the quality of recovery (a subjective 100-point scale) and length of hospital stay after surgery.

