#### H. Sample Size Considerations

The sample size consideration was based on the test for the primary hypothesis that patients who received Naloxegol 25 mg given once in the morning every day will have lower volume of residual urine in bladder when compared to placebo. We would need 62 patients per group [56] to have 90% power at a 2-sided alpha level of 0.05 to detect an effect size of 0.4 or more. The effect size estimation of 0.4 was very conservative as compared to the mean difference of 120 ml (SD: approximate 60 ml) in the volume of residual urine observed by Jose Carlos, I. T., et al [57]. The effect size is the difference in means of the two randomized groups divided by the pooled standard deviation. A maximum of six measurements are planned, twice per day for 3 days. However, we assumed 4 measurements per patients with a correlation of 0.3 to be conservative for the sample size calculation. Considering a loss of follow-up rate of 10%, we will need 12 more patients to reach the planned power with an end sample size of 136. A blinded data quality check will be conducted at 50% (68 patients) of the planned enrollment of 136 patients. In addition to the 136 patients, we will enroll 2 pilot patients to test feasibility of recruitment, protocol adherence, randomization process, and data collection.

SAS software version 9.4 for Windows (SAS Institute, Cary, NC) will be used for all statistical analyses and graphics.

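### The catheterisation outcome has no sparse-data method: if events are rare, logistic regression may give an infinite treatment odds ratio, mainly because one arm has no events

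*Combined protocol and SAP*

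**What the plan says.** Section G, under the secondary and exploratory analysis, compares the arms on "incidence (any versus none) of need for indwelling urinary catheterization (defined as residual urine volume > 400 ml) using logistic regression". This is one of three secondary hypotheses, each tested at 0.017. The same paragraph adds: "All the analyses will be adjusted for imbalanced baseline characteristics, if any".

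The opening of Section G defines imbalance: "Any covariable with a standardized difference greater than 0.2 in absolute value will be regarded as a potential confounder", and such covariates "will be adjusted for when comparing Naloxegol and placebo groups on all the outcomes". No maximum number is set. No exact, penalised or unadjusted alternative is named, and neither is the type of test (Wald, likelihood ratio or score).

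Section E stratifies randomisation on chronic opioid use. The secondary models do not list that factor, so it enters only if it happens to be imbalanced, which stratification is meant to prevent.

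The only rate in the documents that bears on this outcome is in Introduction A: "The true incidence of POUR is unclear but is estimated to vary between 5-70" per cent. It describes postoperative urinary retention in general. Section H sizes the trial for the primary outcome alone.

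**The concern.** The trial is small for a binary outcome, and the exclusion criteria remove patients with known retention, incontinence, other urogenital disease or anticholinergic drugs. A low rate of volumes above 400 ml is therefore possible. With a handful of events and several covariates chosen by chance imbalance, maximum-likelihood logistic regression can separate: one or more coefficients run to infinity, and their standard errors with them.

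The serious case is an infinite treatment coefficient. It arises when one arm has no events, which may be the result most favourable to the drug. A Wald test then gives a P value near 1, while an exact or penalised-likelihood test of the same data can be significant. Because the plan does not say which test applies, the conclusion for Secondary Aim 2 could depend on a choice made after the data are seen.

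**Working it through.** **Inputs from the documents.** 62 evaluable per arm and 136 enrolled, so 68 per arm (Section H); threshold 0.2 (Section G); secondary alpha 0.017 (Section G); low end of the retention range 5% (Introduction A). Section F lists about 18 candidate covariates before laboratory tests: 6 demographic items, tobacco, 10 history items and the Apfel score.

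**Assumptions, not in the documents.** The treated-arm rate (equal to control, or half of it); one third of covariates continuous and the rest binary with 5-50% prevalence; covariates independent.

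**1. The plan's own figure.** Section H states "We would need 62 patients per group [56] to have 90% power at a 2-sided alpha level of 0.05". The standardized difference it assumes is 0.4, on 4 measurements correlated at 0.3. 

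n = 2(1.960 + 1.282)²/0.4² × [1 + 3(0.3)]/4 = 131.3 × 0.475 = 62.4. 

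The stated 62 is reproduced. It says nothing about the catheterisation outcome.

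**2. Covariates admitted by chance.** P(|standardized difference| > 0.2) = 2[1 − Φ(0.2/√(2/n))].
- n = 62: 2[1 − Φ(1.114)] = 26.5%; 18 × 0.265 = 4.8 covariates.
- n = 68: 2[1 − Φ(1.166)] = 24.4%; 18 × 0.244 = 4.4 covariates.

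**3. Events at 5% v 2.5%.** 62 × 0.075 = 4.65; 68 × 0.075 = 5.1. Counting treatment as one further term, that is 4.65/5.8 = 0.8 or 5.1/5.4 = 0.9 events per term.

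**4. Probability that at least one arm has no events.** With A = (1 − p_c)^n and B = (1 − p_t)^n, this is A + B − AB.

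| Control v treated | n = 62 | n = 68 |
|---|---|---|
| 5% v 5% | 8.1% | 6.0% |
| 5% v 2.5% | 0.042 + 0.208 − 0.009 = 24.1% | 0.031 + 0.179 − 0.005 = 20.4% |
| 10% v 5% | 4.3% | 3.1% |
| 20% v 10% | 0.1% | 0.1% |

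**5. Simulation of the rule as written** (800-1,500 trials per setting; separation checked for any coefficient and for treatment alone). The middle column uses 18 candidates.

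| Control v treated | Any coefficient infinite, n = 62 / 68 | Treatment coefficient infinite |
|---|---|---|
| 5% v 5% | 50% / 39% | 6-9% |
| 5% v 2.5% | 65% / 60% | 20-28% |
| 10% v 5% | 29% / 26% | 2-4% |
| 20% v 10% | 6% / 4% | about 0 |
| 37.5% v 18.75% | 0.6% (n = 62) | 0 |

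The last column spans both sample sizes and includes the exact values from step 4. At 5% v 2.5%, varying the number of candidates from 5 to 25 moves the any-coefficient share between 37% and 72%; other prevalences or prognostic strengths give 54-70%. At 20% v 10%, other covariate mixes raised it to as much as 16%. Steps 4 and 5 together show that the covariates add at most about 3 percentage points to infinite treatment estimates.

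**6. What a zero-event arm does to the test.** Take 0 of 68 v 7 of 68, unadjusted. Fisher P = 0.013 and Firth profile-likelihood P = 0.005, both below 0.017. The maximum-likelihood fit does not converge: after 12 Newton steps the log odds ratio is −11.0 with standard error 89.3, so Wald P = 0.90.

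**7. The proposed remedy.** At 5% v 2.5% with 62 per arm, Firth gave finite treatment estimates in 1,500 of 1,500 trials unadjusted and in 1,499 of 1,500 with the imbalance covariates kept. The median log odds ratio was −0.60 to −0.62 against a true ln(0.025/0.975) − ln(0.05/0.95) = −0.72. Approximate power at alpha 0.017 is Φ(0.025/√[(0.0475 + 0.0244)/62] − 2.387) = Φ(−1.65), about 5%.

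**The case against.** **The rate may not be low.** The outcome counts any qualifying scan over several days in patients who all receive opioids, and 5% is only the floor of a very wide range for a related condition. From about 20% upward the treatment estimate is safe. This stands. It makes the point conditional, but it also argues for a method that is valid across the whole range, since the plan commits to no rate.

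**The covariates are not the main culprit.** A reader might infer from the half-to-two-thirds figure that the imbalance rule leaves Secondary Aim 2 without an odds ratio in most trials at 5%. The calculations do not support that. Most of those infinite coefficients belong to nuisance covariates and leave the treatment coefficient finite. Firth also copes with the imbalance covariates left in. Replacing them is therefore not needed to cure separation; the reason to do so is to have a small model fixed in advance.

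**The plan says only logistic regression.** It does not commit to maximum likelihood or a Wald test, and Firth is available in the SAS 9.4 software it names. This is correct: the gap is silence, not a stated choice of a failing method.

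**The any-symptom outcome.** A reader might infer that it fails in the same way because nearly every patient has a symptom. The documents give no rate for it, so this cannot be claimed.

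**Conclusion.** The point holds as a conditional gap in pre-specification. If the event rate is about 5% in controls and half that on treatment, the treatment odds ratio is infinite in about one trial in five to slightly more than one in four. With 5% in both arms it is 6-9%; at 10% v 5% it is 2-4%; at 20% v 10% the problem is gone. The cause is almost wholly an arm without events. The uncapped covariate rule adds non-finite nuisance terms and little more.

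These figures rest on the assumed treated-arm rates and covariate mix, and on applying the low end of a general retention range to the above-400 ml outcome. At about 5 events the comparison has little power whatever estimator is used. The correction is worth making because the outcome is formally tested and the remedy is small, but it does not touch the primary analysis.

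**What to change.** For the catheterisation outcome, pre-specify:
- Firth-penalised logistic regression (FIRTH option of PROC LOGISTIC, SAS 9.4), with profile-likelihood P value and confidence interval.
- Treatment and chronic opioid use, the stratification factor, as the fixed model terms, in place of covariates selected by imbalance.
- The risk difference with a score-type 95% interval (Newcombe or Miettinen-Nurminen), which can be computed even if one arm has no events.

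The same method may be named for the any-symptom outcome, as a precaution only.

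Cost: about two lines of text and one software option. The odds ratio is shrunk somewhat toward 1 (median log odds ratio about −0.61 against a true −0.72 at 5% v 2.5%). Power does not improve, and the results text should say so if events turn out to be few.

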#### E. Protocol

Patients must meet all inclusion and exclusion criteria to be eligible for the study. After eligibility is confirmed, patients will receive complete information about the study both verbally and in writing. Informed consent must be obtained from the patients prior to randomization and study-specific procedures.

Anesthetic management will follow pre-established clinical and institutional guidelines. Patients can be pre-medicated and will receive spinal or general anesthesia per institutional routine according to attending anesthesiologist discretion. Spinal anesthesia will include the standard monitoring for the given operation, and will occur after the electrocardiogram and monitoring equipment are placed on the patient. Prophylactic antibiotics will be given per surgical routine. During the induction of general anesthesia, indwelling urinary catheters will be inserted only in the patients with operation time exceeding 3 h or who required meticulous monitoring of the intraoperative fluid status. Intraoperative and postoperative fluid management will be left to discretion of the clinicians, who will be administrating them using institution standards.

Randomization (1:1) will be web-based and initiated prior to conclusion of surgery; allocation will thus be concealed from investigators. Randomization will be stratified based on chronic opioid use (if present) to ensure balance between treatment groups within chronic opioid users and nonusers. Chronic opioid use will be defined as opioid use for more than 30 consecutive days, at a daily dose of 15 mg or more of morphine or equivalent, within the 3 months before surgery. The treatment groups will be oral Naloxegol and placebo.

Naloxegol or placebo will be administered starting the first morning of surgery and continued for two postoperative days or until hospital discharge (whichever occurs first) with 25 mg (or equivalent size and shape of Placebo). The post-operative study drug doses will be given in the morning 1 hour before or 2 hours after the morning meal. Intraoperative and postoperative pain medications will be left to discretion of the anesthesiologist.

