#### Primary analysis.

We will test the primary hypothesis that subjects who received Naloxegol 25 mg given once in the morning every day will have lower volume of residual urine in bladder when compared to placebo. We will compare the randomized groups on the volume of residual urine in bladder, which will be measured twice per day for up to 3 days (i.e., a maximum of 6 measurement times in total), using a linear mixed model adjusting for the within-subject correlation (using an autoregressive correlation structure). At each measurement time, the average of the measurements will be analyzed. Any imbalanced baseline characteristics and volume of residual urine in bladder prior to the procedure will be included as covariates in the model. If the group-by-time interaction is non-significant (P > 0.20), we will assess the group difference on the volume of residual urine across over all the measurements. In the presence of a group-by-time interaction, the group difference will be assessed separately at each measurement time and a Bonferroni correction will be made for multiple comparisons to maintain the hypothesis-wise 2-sided type I error at 0.05 (the significance criterion will be 0.05 / 6).

Second, we will assess the treatment effect within chronic opioid users and nonusers using the same statistical methods as above. The significance level will be 0.025 for each of the two subgroup analyses (Bonferroni correction).

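### The fixed Bonferroni level of 0.05/3 for the three secondary hypotheses is valid, but Holm's procedure would keep the same family-wise bound and can reject more

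*Combined protocol and SAP*

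**What the plan says.** Section G (Data Analysis), under Secondary and exploratory analysis, defines the family: "We will test the following three secondary hypotheses". The three are opioid-related side effects (any versus none, logistic regression), need for indwelling catheterization (any versus none, logistic regression) and the Quality of Recovery scale (linear mixed model). The decision level follows: "The hypothesis-wise 2-sided type I error for each of the secondary outcome will be controlled at 0.017 (i.e., 0.05/3, Bonferroni correction". Neither protocol nor SAP text mentions a stepwise procedure for this family.

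The primary analysis, where it corrects over measurement times, leaves its criterion as a fraction: "the significance criterion will be 0.05 / 6".

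Section H (Sample Size Considerations) sizes the trial on the primary hypothesis alone, "to have 90% power at a 2-sided alpha level of 0.05 to detect an effect size of 0.4 or more". No secondary outcome has an effect size, an event-rate assumption or a power statement.

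**The concern.** Under the stated rule, each secondary p-value faces 0.05/3 whatever happens to the other two. Once one hypothesis has been rejected, at most two true null hypotheses can remain, so testing the rest at 0.05/3 is stricter than a family-wise level of 0.05 requires. Holm's procedure uses that slack. It needs no ordering of the outcomes, no independence assumption and no extra data.

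At stake is power for the second and third secondary claims in a trial that was not sized for any of them. A result with p-values of, say, 0.01, 0.02 and 0.04 (invented for illustration) would give one secondary finding under the plan and three under Holm.

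**Working it through.** **Inputs.** Three hypotheses, 2-sided, family level 0.05, Bonferroni (section G). Effect sizes and correlations among the secondary tests are not in the documents and are assumed below.

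**1. The plan's own figure.** 0.05/3 = 0.016667, which is 0.017 to three decimals. The printed level reproduces.

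**2. Holm rejects everything Bonferroni rejects.** Order the p-values and compare the smallest with 0.05/3, the next with 0.05/2 and the last with 0.05, stopping at the first failure. Every threshold is at least 0.05/3, so any p-value at or below 0.05/3 is also rejected by Holm.

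**3. Holm keeps the bound.** Let m0 null hypotheses be true. The first false rejection comes at a step whose threshold is at most 0.05/m0, so it requires some true-null p-value to be at or below 0.05/m0. Summing over the m0 true nulls gives at most m0 × 0.05/m0 = 0.05, whatever the dependence. As a check, family-wise error was simulated with all three nulls true (1,000,000 runs): 0.0492, 0.0475 and 0.0421 at correlations 0, 0.3 and 0.6. Bonferroni at 0.05/3 gives the same values, because the first step is the same. The exact independent value is 1 − (1 − 0.05/3)³ = 0.0492.

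**4. Size of the gain (assumed effects).** Take three real effects, each with 80% power at an unadjusted 2-sided 0.05. Each test statistic then has mean 1.960 + 0.842 = 2.802. Power per outcome at a given level is Φ(2.802 − critical value): 0.8000 at 0.05, 0.7123 at 0.025 and 0.6582 at 0.05/3.

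Closed form for independent tests:
- Bonferroni, all three: 0.6582³ = 0.285.
- At least one, either method: 1 − (1 − 0.6582)³ = 0.960.
- Holm, all three: write a = 0.6582, b = 0.7123 − 0.6582 = 0.0541 and c = 0.8000 − 0.7123 = 0.0877. Then a³ + 3a²(b + c) + 3ab² + 6abc = 0.2852 + 0.1843 + 0.0058 + 0.0187 = 0.494.

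Simulation with equicorrelated normal test statistics (500,000 runs per row; Bonferroni at 0.05/3 / Holm):

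| Power at unadjusted 0.05 | Correlation | Average power per outcome | All three | At least one |
|---|---|---|---|---|
| 80% | 0 | 0.66 / 0.75 | 0.29 / 0.49 | 0.96 / 0.96 |
| 80% | 0.3 | 0.66 / 0.74 | 0.36 / 0.55 | 0.91 / 0.91 |
| 80% | 0.6 | 0.66 / 0.73 | 0.45 / 0.61 | 0.85 / 0.85 |
| 50% | 0 | 0.33 / 0.38 | 0.04 / 0.11 | 0.70 / 0.70 |
| 50% | 0.6 | 0.33 / 0.39 | 0.14 / 0.25 | 0.54 / 0.54 |
| 90% | 0 | 0.80 / 0.88 | 0.52 / 0.72 | 0.99 / 0.99 |
| 90% | 0.6 | 0.80 / 0.86 | 0.64 / 0.78 | 0.94 / 0.94 |

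**5. Only one real effect** (80% power, correlation 0.3): its power is 0.658 with Bonferroni and 0.660 with Holm.

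**6. The rounded decimal.** Taken literally, 0.017 would give a sum of 3 × 0.017 = 0.051. The actual family-wise error would be 1 − (1 − 0.017)³ = 0.0501 for independent tests and, by simulation, 0.0484 and 0.0429 at correlations 0.3 and 0.6. Only a p-value between 0.01667 and 0.0170 could be decided differently.

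**The case against.** The strongest reply is that nothing here is wrong. The plan names the family, the sidedness and the correction in advance, and Bonferroni controls the family-wise error. The existence of a more powerful procedure does not make a valid one a defect. That stands, and it is why this is only a suggestion.

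The second reply is that the benefit is assumed. Three real effects with 80% power each is a setting that favours Holm. The outcomes probably overlap, since the symptom scale asks about difficulty passing urine and both questionnaires ask about nausea. Positive correlation narrows the gap in winning all three, from 0.29 against 0.49 at correlation 0 to 0.45 against 0.61 at 0.6. This also stands. The figures illustrate the gain and do not predict it for this trial.

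Third, Bonferroni offers something in return. Its simultaneous intervals are simple: each is a 98.33% interval, from 1 − 0.05/3. When one effect is real and two nulls are true, its error is bounded by 2 × 0.05/3 = 0.033, whereas Holm may use up to 0.05. The plan does not ask for that extra strictness, but Holm is not wholly free.

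A reader might also infer that the plan overspends its alpha, because 3 × 0.017 = 0.051. The documents do not support this. The same sentence gives the rule as 0.05/3, and the primary analysis likewise works in fractions of 0.05. The decimal is rounding for display.

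**Conclusion.** The secondary testing rule is valid but less efficient than it could be. Holm's procedure has the same bound of 0.05 under any dependence and can only add rejections; that much needs no assumption about this trial. The size of the gain does: with three real effects at 80% unadjusted power and correlations of 0 to 0.6, it is roughly 7 to 9 percentage points in average power per outcome and 16 to 21 points in the chance of winning all three.

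Two further inferences would go too far. Holm does not hold the error at exactly 0.05; it holds it at or below 0.05. Nor does the fixed split cost power in every situation: Holm's first step is the same 0.05/3, so the chance of at least one secondary success is unchanged, and with a single real effect the gain is negligible. The point is minor and does not threaten any conclusion the trial might draw under its present rule.

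**What to change.** Before unblinding, replace the sentence on the secondary type I error with one such as: *The three secondary hypotheses will be tested by Holm's procedure at a family-wise 2-sided level of 0.05; the smallest p-value is compared with 0.05/3, the next with 0.05/2 and the last with 0.05, stopping at the first that fails. Thresholds are used unrounded.*

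The cost is one sentence in an amendment, with no patients, data or new models. The plan should also say which confidence intervals will accompany the secondary results, because intervals that match Holm's decisions are less simple than Bonferroni intervals. If the sponsor prefers to keep Bonferroni for that reason, it is enough to drop the rounded decimal and write the criterion as 0.05/3.
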